4.3 Dose and Administration

The netupitant doses to be tested in the pediatric population will match exposures to adult doses of 100 up to 300 mg as tested in pivotal Phase 2 trial NETU-07-07 [20], and 300 mg as tested in pivotal Phase 3 trials (NETU-08-08 [21] and NETU-10-29 [22]. These doses proved to be safe and effective. Basic assumption behind this choice is that efficacious netupitant AUC values in children are similar to those observed in adults at effective doses.

In order to predict the pediatric doses matching exposures to adult doses of 100 and 300, CL/F values in different age classes were estimated by pharmacokinetic allometry scaling according to the following model:

$$(CL/F)p = (CL/F)a * \left(\frac{BWp}{70}\right)^{ADE}$$

where (CL/F)p and (CL/F)a are the systemic clearances in pediatric patients and adults, respectively, BWp is the body weight of children, 70 is the standard adult BW expressed in kg, and ADE is an age-dependent exponent [24]. ADE values across the age classes were assumed to be the following [24]: 1.2 for children aged \leq 3 months, 1.0 for those aged \geq 3 months to 2 years, 0.9 for those aged \geq 2 years to 5 years, and 0.75 for those aged \geq 5 years. The model accounts for the effect of the body size change and organ maturation. An age-dependent exponent that decreases with the age increase, is consistent with a faster functional maturation occurring during the youngest age ranges.

Reference body weights for children were taken from growth charts compiled by the CDC (Centers for Disease Control and Prevention, Atlanta, GA, USA) [25].

Average AUC values in adults receiving 100 and 300 netupitant have been calculated by dividing these doses by the geometric mean of netupitant clearance in adults, (CL/F)a = 20.27 L/h, obtained from the population PK study (Study NETU-10-02 [26]), assuming linear kinetics. The netupitant doses for each pediatric age classes that are expected to yield these target AUC values have been calculated by multiplying AUCs by

the respective predicted CL/F in children, assuming the same netupitant oral bioavailability (F) in pediatric patients and adults.

In conclusion, netupitant doses per age class to be tested in the PK/PD-based dose finding study in pediatric patients resulted to be the following:

Age class	Dose 1 (mg/kg)	Dose 2 (mg/kg)
Birth to < 1 month	0.8	2.4
1 month to < 3 months	0.8	2.4
3 months to < 6 months	1.33	4
6 months to < 12 months	1.33	4
1 year to < 2 years	1.33	4
2 years to < 5 years	1.33	4
5 years to < 12 years	1.33	4
12 years to < 18 years	1.33	4
ADULTS and children with BW ≥ 75 kg	100 mg	300 mg

Patients enrolled in each of the two treatment groups will receive a single oral dose of netupitant per kg body weight as described in Section 4.2 Treatment Groups, 1 h (\pm 10 minutes) prior to start of emetogenic (HEC or MEC) chemotherapy on Day 1 and a single oral dose of palonosetron at the dosage of 20 µg/kg (maximum 1.5 mg), immediately (within 5 minutes) after netupitant, i.e., 1 h (\pm 10 minutes) prior to start of emetogenic (HEC or MEC) chemotherapy on Day 1.

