1.4 Study Rationale

This study (NEPA-15-31) will be a Phase 2 PK/PD dose-finding study of oral netupitant administered concomitantly with oral palonosetron in pediatric cancer patients for the prevention of nausea and vomiting associated with emetogenic chemotherapy. This will be part of the pediatric program of the oral NEPA FDC's line extension, aiming at complying with the post-approval commitments after registration of oral NEPA FDC (Akynzeo®) by US FDA.

The selection of the netupitant doses to be used in this study is supported by efficacy and safety data in adults from Akynzeo® pivotal studies NETU-07-07 (HEC) [20] and NETU-08-18 (MEC) [21]. In those studies, the efficacy and safety of oral netupitant doses of 100, 200 and 300 mg (NETU-07-07 [20]) and 300 mg (NETU-08-18 [21] and NETU-10-29 [22]) in combination with oral palonosetron (0.5 mg) were assessed.

During the development of oral Akynzeo[®], netupitant doses of 100, 200, 300 and 450 mg have been tested in the adult population (see studies NP16601, NP16603, NETU-06-27, NETU-06-07, NETU-07-01, NETU-10-29). All doses proved to be well tolerated and doses of 100 and 300 mg showed antiemetic efficacy in pivotal clinical trials in cancer patients undergoing emetogenic chemotherapy treatments. [16, 20, 21, 22]

In this study (NEPA-15-31), the following two different netupitant dosages will be tested in patients aged from 3 months to < 18 years: 1.33 mg/kg up to a maximum of 100 mg, and 4 mg/kg up to a maximum of 300 mg. Because netupitant elimination is mainly mediated by CYP3A4 metabolism, due to CYP3A4 ontogeny (where CYP3A4 capacity in 12 month olds is about 40% of adult levels), the youngest patient age classes (< 3 months of age) will be treated at lower doses: i.e., 0.8 mg/kg and 2.4 mg/kg. All

netupitant doses in all age classes will be concomitantly administered with palonosetron 20 μg/kg (up to a maximum dose of 1.5 mg).

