8.1 Sample Size Determination

A total of 92 pediatric patients (i.e., 46 for each treatment group) will be enrolled in the study.

For each age class used for stratification, a sample size was computed. Each age class is powered to target a 95% confidence interval within 60% and 140% of the geometric mean estimate of clearance with at least 80% power.

The sample size was computed for the following age classes: Birth-<1 month, 1 <3 months, 3-<6 months, 6-<12 months, 1-<2 years, 2-<5 years, 5-<12 years, 12-<18 years.

Variability of clearance in each pediatric age class was estimated based on the same model used to determine the dose to be administered, which is:

$$Log(CL/F)p = log(CL/F)a + ADE * log(BWp/70)$$

where (CL/F)p and (CL/F)a are the systemic clearances in pediatric patients and adults, respectively, BWp is the body weight of children and ADE is an age-dependent exponent considered constant within each age class.

Variance of log (CL/F)p was then calculated as:

ADE² * Variance (log (BWp))

considering log (CL/F)a as a constant term.

Variance (log (BWp)) was obtained from published data in Fryar et al 2012 [31], where mean values in each age class and related standard errors were available.

Based on these data, the variance of log weight was obtained as:

Variance (BWp) = standard error $^2 * N$

and

Variance (log BWp) \approx Variance (BWp) / Mean²

(i.e., no assumption on the statistical distribution was made);

The table below reports the values as selected from published data in Fryar et al 2012 [31] and the further elaboration

Age class planned for the study	Age class [31]&	Weight (kg) N/ Mean / SE / gender [31]	ADE	Estimated SD (BWp)	Estimated SD (log BWp)	Estimated SD (log CL/F)
Birth to <1 month	Birth-2 months	82 / 5.0 / 0.11 / F	1.2	1.00	0.199	0.239
1 to <3 months	Birth-2 months	82 / 5.0 / 0.11 / F	1.2	1.00	0.199	0.239
3 to <6 months	3-5 months	111 / 7.1 / 0.11 / M	1	1.16	0.163	0.163
6 to <12 months	6-8 months 9-11 months	103 / 8.7 / 0.13 / M 108 / 9.6 / 0.15 / M *	1 1	1.32 1.56	ND 0.162	ND 0.162
1 to <2 years	1 year	297 / 10.9 / 0.10 / F	1	1.72	0.158	0.158
2 to <5 years	3 years	191 / 15.7 / 0.24 / F	0.9	3.32	0.211	0.190
5 to <12 years	9 years	191 / 36.6 / 1.17 / M	0.75	16.2	0.442	0.331
12 <18 years	17 years	188 / 77.4 / 2.41 / M	0.75	33.0	0.427	0.320

[&]amp; only data related to the age period actually used for the sample size calculations are reported in this table.

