Sample size was then computed by the R program described in Wang et al 2012 [32] for each age class.

The resulted sample size for each treatment group, and the relevant power are provided in the table below:

Age class for the study	N estimated / dose	Power
Birth to < 1 month	6	0.891
1 to <3 months	6	0.891
3 to <6 months	4	0.832
6 to <12 months.	4	0.836
1 to <2 years	4	0.854
2 to <5 years	5	0.913
5 to <12 years	8	0.830
12 to <18 years	8	0.865

In order to facilitate the management of the study, the calculated sample size in the age class 2 to <5 years will be rounded up to 6 patients.

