8.3.5 Efficacy Analyses

All results will be interpreted in a descriptive manner, since the study is not powered to compare the treatment groups for the efficacy assessments.

For each phase (delayed, acute, and overall), numbers and percentages (including 95% CI) of patients with CR, with no emetic episodes and no rescue medication will be summarized by treatment. The difference in response rate between the groups and relevant 95% CI will be provided as well.

Efficacy analysis will be presented for the overall population and by strata.

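### The Section 4.3 dose table is not the output of its own allometric model: at the Section 8.1 weights, predicted AUC is about 80% (2 to <5 years) and 79% (5 to <12 years) of the adult target

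*Protocol*

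**What the plan says.** Section 4.3 opens with the design property: "The netupitant doses to be tested in the pediatric population will match exposures to adult doses of 100 up to 300 mg". It then gives the method. Pediatric clearance is (CL/F)p = (CL/F)a × (BW/70)^ADE, with (CL/F)a = 20.27 L/h. ADE is 1.2 up to 3 months, 1.0 from 3 months to 2 years, 0.9 from 2 to 5 years and 0.75 from 5 years. Adult target AUCs are 100 mg and 300 mg divided by 20.27 L/h, under linear kinetics and equal bioavailability. On the dosing rule it says "The netupitant doses for each pediatric age classes that are expected to yield these target AUC values have been calculated by multiplying AUCs by" the predicted pediatric clearance.

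The table is introduced as the outcome: "In conclusion, netupitant doses per age class to be tested in the PK/PD-based dose finding study in pediatric patients resulted to be the following". It lists 0.8 and 2.4 mg/kg below 3 months, and 1.33 and 4 mg/kg for every class from 3 months to <18 years, capped at 100 and 300 mg from 75 kg. No rounding step, simplification or tolerance for a match is given.

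Section 8.1 says that it uses the same model. It prints weight data as N / mean / SE / sex: "191 / 15.7 / 0.24 / F" for 2 to <5 years and "191 / 36.6 / 1.17 / M" for 5 to <12 years.

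**The concern.** Three exponents apply from 3 months upward, but there is only one mg/kg value per arm. Under the stated rule the dose is proportional to BW^ADE, so dose per kg is constant only if ADE = 1. For the classes with ADE 0.9 and 0.75, the printed doses therefore cannot come from the printed calculation.

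Section 4.3 justifies the two dose levels by assuming that effective AUCs in children resemble those in adults at effective doses. Section 1.4 says that "doses of 100 and 300 mg showed antiemetic efficacy in pivotal clinical trials". If the model predicts AUCs clearly below the adult 100 mg value for dose 1 in some classes, the stated property fails there by the protocol's own reckoning. A reader who is told that exposures match could also misread the response rates by age class, since Section 8.3.5 says: "Efficacy analysis will be presented for the overall population and by strata".

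**Working it through.** **Inputs.** From Section 4.3: (CL/F)a = 20.27 L/h, reference weight 70 kg, ADE by age, doses of 1.33 and 4 mg/kg (0.8 and 2.4 below 3 months), caps of 100 and 300 mg. From Section 8.1: mean weights 5.0, 7.1, 9.6, 10.9, 15.7, 36.6 and 77.4 kg.

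**Reading check.** SE × √N, divided by mean weight and multiplied by ADE, should return the Section 8.1 SDs of log clearance.
- 2 to <5 years: 0.24 × √191 = 3.32; 3.32/15.7 = 0.211; × 0.9 = 0.190, as printed.
- 5 to <12 years: 1.17 × √191 = 16.2; 16.2/36.6 = 0.442; × 0.75 = 0.331, as printed.

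The weights and exponents are therefore read correctly.

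**Targets.** 100/20.27 = 4.933 and 300/20.27 = 14.800 mg·h/L.

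**General ratio below the cap.** Adult clearance cancels:
- Dose 1: (1.33 × 70/100) × (BW/70)^(1−ADE) = 0.931 × (BW/70)^(1−ADE)
- Dose 2: (4 × 70/300) × (BW/70)^(1−ADE) = 0.933 × (BW/70)^(1−ADE)

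With ADE = 1 this is a constant 0.93. With ADE below 1 it falls as weight falls.

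**The two classes.**
- 15.7 kg, ADE 0.9: CL/F = 20.27 × (15.7/70)^0.9 = 5.279 L/h. AUC = 1.33 × 15.7/5.279 = 3.955 and 4 × 15.7/5.279 = 11.896 mg·h/L.
- 36.6 kg, ADE 0.75: CL/F = 20.27 × (36.6/70)^0.75 = 12.464 L/h. AUC = 1.33 × 36.6/12.464 = 3.906 and 4 × 36.6/12.464 = 11.746 mg·h/L.

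**Predicted AUC as a share of the adult target, all classes**

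| Age class (weight) | ADE | Dose 1 | Dose 2 |
|---|---|---|---|
| <3 months (5.0 kg) | 1.2 | 0.949 | 0.949 |
| 3 months to <2 years (7.1–10.9 kg) | 1.0 | 0.931 | 0.933 |
| 2 to <5 years (15.7 kg) | 0.9 | 0.802 | 0.804 |
| 5 to <12 years (36.6 kg) | 0.75 | 0.792 | 0.794 |
| 12 to <18 years (77.4 kg, capped) | 0.75 | 0.927 | 0.927 |

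Multiplying by 100 and 300 mg gives adult-equivalent doses of about 80 and 241 mg at 15.7 kg, and 79 and 238 mg at 36.6 kg.

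**Other weights.** With the cap, the ratio peaks near 75 kg: 0.938/0.940 (dose 1/dose 2) at ADE 0.9 and 0.948/0.950 at ADE 0.75. For assumed weights of 11–20 kg (2 to <5 years) it is 0.77–0.82. For assumed weights of 18–45 kg (5 to <12 years) it is 0.66–0.84.

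**A 75 kg reference.** Since 1.33 ≈ 100/75 and 4 = 300/75, a 75 kg divisor may lie behind the table. It brings 3 months to <2 years to about 1.00, but leaves 0.853/0.855 at 15.7 kg and 0.834/0.836 at 36.6 kg.

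**Patients affected.** Section 3.3.1 plans 12 + 16 = 28 of 92 patients in the two classes. That is 6 + 8 = 14 per arm, where the 6 reflects the Section 8.1 statement that "the calculated sample size in the age class 2 to <5 years will be rounded up to 6 patients".

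**The case against.** **The weights.** Section 4.3 took its weights from CDC growth charts and does not print them. The Section 8.1 weights come from another source, at one year of age and one sex per class. This stands: 80% and 79% are specific to those weights. The conclusion is not, because the ratio stays at or below 0.95 at every weight once ADE is 0.9 or 0.75.

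**A common shortfall.** About 7 points also appear at 3 months to <2 years and fit a 75 kg divisor. Relative to that level, the two classes are at about 0.86 (0.802/0.931) and 0.85 (0.792/0.931). This is fair, but a gap of about 15% remains unexplained, and 75 kg contradicts the printed 70 kg.

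**The wording.** No tolerance defines a match, and Section 4.3 also speaks of similar AUCs and of a 100 to 300 mg range. Dose 2 does stay inside that range. Dose 1 falls below its lower end, and no tolerance rescues the statement that the table resulted from the calculation.

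**The consequence.** This is the strongest objection, and most of it stands. Individual exposures will be estimated from the children's own samples (8.3.4) and compared with adults (8.3.6), so a poor prediction would be detected. Both arms are scaled alike, so their contrast within a class is intact. The rates by stratum are descriptive and imprecise: 4 responders of 8 gives an exact 95% CI of about 16–84%. The effect on reading 8.3.5 is therefore minor.

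**Conclusion.** The point holds. The Section 4.3 table is not the output of the model that Section 4.3 describes, and the exposure-matching claim is wrong as written for 2 to <5 and 5 to <12 years. Predicted AUC there is about 80% and 79% of the adult target at the Section 8.1 weights, and roughly 66–84% over the assumed weight ranges. For dose 1 this lies below the adult 100 mg exposure. For dose 2 it corresponds to about 240 mg, not 300 mg. Patients of 12 years and over who weigh less than 70 kg also fall below 93%.

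The result rests only on the protocol's own model, its 70 kg reference and linear kinetics. It says nothing about which dose is appropriate, nor that exposure below the adult 100 mg value is ineffective. Sample size, conduct and the 8.3.6 regression are unaffected. The defect is a stated design property that the stated model does not deliver, and it should be corrected.

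**What to change.** In Section 4.3, reconcile the model, the matching claim and the dose table. Either show the calculation that yields the table, including the weights and any rounding or change of reference weight, or state that the table is not the model output and say how it was set. Replace the matching claim with a small table of predicted AUC ratios to adult 100 and 300 mg for each age class, with the weights used. Add a sentence to Section 8.3.5 that results by age class are to be read alongside those ratios. Section 8.3.6 needs no change, and no dose is proposed here.

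The cost is text and one table, with no change to sample size, conduct or analysis. The price is that the stated exposure match will look less favourable than it does now.

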4.4 Packaging and Shipment

The investigational products (netupitant vials and palonosetron vials) will be provided in sealed and appropriately labeled study kits. The netupitant vials included in the kits will have the same appearance for all the dosages; the different concentrations of the active pharmaceutical ingredient (API) permit to have different netupitant dosages by using the same volume, which is weight-based defined.

Packaging and labeling of the study drugs will be carried out in accordance with all applicable regulatory/legal requirements by CSM Europe SA (previously B&C Group) (Belgium).

Study kit is inside of a carton box and contains 2 vials of palonosetron (up to 1.5 mg dosage), 1 vial netupitant suspension and the ancillaries to be used for the collection and administration of the drugs. All the components of the study kits are identifiable with differently colored labels.

The procedure to be followed for the preparation and administration of the drugs will be included in the Drug Manual provided to the site staff before the start of the study (also refer Section 4.8 Randomization, Blinding and Assignment of Study Drug).

The study kits will be delivered either to a designated person at the site's Pharmacy or directly to the Investigator or designated staff, as applicable.

4.5 Storage

The study drug will be delivered and stored at room temperature (below 25°C), in a secure area with limited access and protected from direct light. At the study site, the designated responsible person for storage of the investigational product (the site pharmacist or the Investigator or a designee) should also make sure that the drugs are kept separately from the other medications available on site and in no circumstance should be mixed up with any other medications used at the trial site.

4.6 Drug Depots

The study drugs kits will be shipped from the central depot to either local drug depots, or directly to the study sites, as applicable.

4.7 Accountability

Once the kits are received at the study site, the pharmacist or designated responsible person will sign a drug receipt form. Adequate records of the receipt, dispensation and return of study drugs must be maintained throughout the study. Used study drug kits will be retained until the drug accountability has been checked by a designated monitor; a peel-off portion of the study drug label will also be affixed to the drug preparation form as an additional accountability measure in case internal policies require immediate disposal of the vials. Unused study drug kits remaining at investigational sites at the end of the study will be returned to the drug depots for destruction or will be destroyed at the sites as applicable. At the end of the study, delivery records will have to be reconciled with those of used and returned stocks. Any discrepancy will have to be accounted for. Destruction of unused medication will be documented in writing according to FDA IND regulation 21CFR312.59, ICH Good Clinical Practice (GCP) and the drug depot Standard Operating Procedures (SOPs). Any destruction of remaining study drugs material is to be first approved in writing by the study Sponsor.

4.8 Randomization, Blinding and Assignment of Study Drug

Randomization will be used to avoid bias in assigning patients to treatment and to increase the likelihood that known and unknown patient attributes are evenly balanced across treatment groups.

A computer-generated list of the kit numbers ("packaging list") will be prepared by the Contract Research Organization (CRO) to allow for blinding of the two treatment groups. Sealed cartons (kits) containing the study drugs will be prepared according to this packaging list. An appropriate amount of treatment kits will be supplied to the designated person at the investigational sites at the beginning of the study, with further re-supplies scheduled once the number of available treatment kits decrease to a pre-set threshold at each site. Kits are indistinguishable, i.e., the netupitant vials contained in the kits have the same appearance for all the dosages; the different concentrations of the API permit to

have different netupitant dosages by using the same volume, which is weight-based defined.

The computer-generated patient randomization list(s) will be prepared by the CRO to allow for random treatment allocation where/when a random treatment allocation is foreseen. The Interactive Web Response System (IWRS) provider and a designated person at Helsinn will retain master copies of the packaging and patient randomization lists in a secure fashion to maintain the blind.

Sponsor project team members and members of the Investigator's team will not have access to the lists. Patients will enter the study according to the design described in Section 3.1 Study Design and in Appendix 1.

Randomization/treatment assignment of eligible patients will be done using IWRS integrated with EDC system. Patients will be registered in the EDC at screening visit, and patient identification number will be automatically assigned by the system. Once a patient fulfills the inclusion and exclusion criteria, at Day 1 (Visit 2) the Investigator will ask for randomization/treatment assignment through the EDC. The patient's date of birth, the emetogenicity and the schedule of the chemotherapy (all the information is necessary for identifying the patient's strata) and the body weight (necessary to establish the total dosages of netupitant and palonosetron to be administered) are taken into consideration. These and other demographic data are stored in the IWRS module, together with the assigned treatment.

The IWRS will assign the treatment to be administered to the patient through a static central blocked randomization for patients to be randomized and treated in a double-blind fashion. The IWRS will assign the treatment to be administered to the patient in the youngest age classes (all age classes < 12 months) according to the study design, i.e. the lowest netupitant dose(s) will be assigned and evaluated before escalating to the subsequent netupitant dose groups.

Using the assigned dosage and the patient's weight, IWRS will customize patient-specific instructions for study drug preparation and send them to designated person at the study site.

The designated person at site will prepare the study drug following the instructions provided by the IWRS.

The IWRS will be open for randomization / treatment assignment only for the age-class(es) that are allowed to include patients, according to the design and to the DSMB decisions. The IWRS will be closed for each age class once the relevant number of enrolled patients reached the planned target number of patients.

4.8.1 Emergency Unblinding Procedure

As all patients will be treated with netupitant, it is unlikely that knowledge of the specific doses administered to an individual patient will provide sufficient additional information to the Investigator to warrant breaking the blind for the patient.

However, if the Investigator considers it essential to know the dose of netupitant administered in order to adequately respond to a medical emergency, the Investigator can obtain the treatment assignment of an individual patient through the IWRS. If possible, the Investigator should discuss with the CRO Medical Monitor whether unblinding is essential prior to contacting IWRS for the unblinding of the patient's treatment assignment.

In case of unblinding, the Sponsor and CRO will be notified in a blinded fashion immediately through an automatic communication of the IWRS. Moreover, the Investigator should notify the CRO Medical Monitor and the Sponsor Drug Safety within 24 h of the performed emergency unblinding.

If the blind is broken for an individual patient, the Investigator must record the following information in the patient's source documents:

- The date and time the blind was broken.
- The reason the blind was broken

In case of unblinding by the Investigator, the patient will be withdrawn from the study.

If the blind is broken by the Sponsor (via IWRS) for pharmacovigilance reporting purposes in case of a suspected unexpected serious adverse reaction (SUSAR), the blind will be maintained for all other persons involved in this study. The patient will not be withdrawn from the study in case of unblinding by the Sponsor's Drug Safety Unit for pharmacovigilance reporting purposes.

Any unblinding will be performed through IWRS (24-h coverage), and the unblinding procedure is described in detail in the IWRS instruction manual that will be provided separately. For the DSMB the unblinding process is described in the DSMB charter.

